	
 
• Change in cDLQI from baseline to Weeks 16 and 24 for participants <16 years of age at baseline
 
• Percentage of participants with a DLQI of <math>\geq 4</math> points at baseline who achieve a <math>\geq 4</math>-point improvement in DLQI at Weeks 16 and 24 for participants <math>\geq 16</math> years of age at baseline
 

Exploratory
	

 
• To evaluate the efficacy and health outcome measures of lebrikizumab from baseline by visit in participants with skin of color and moderate-to-severe AD
 
	
 
• Percentage change in PO-SCORAD from baseline by visit
 
• Change in Post-inflammatory Dyschromia Scale from baseline by visit
 
• Percentage change in ADCT from baseline by visit
 
• Using WPAI-AD by visit, change in baseline in             
 
○ absenteeism in those who are currently employed (working for pay)
 
○ presenteeism in those who are currently employed (working for pay)
 
○ overall work impairment in those who are currently employed (working for pay), and
 
○ impairment in activities (all participants)
 
 
 
• Percentage of participants with an F-IGA score of 0 or 1 and a reduction <math>\geq 2</math> points from baseline by visit
 
• Lichenification change from baseline (calculated from EASI)
 
• Participant satisfaction change from baseline (1 question)
 
• Percentage of participants achieving EASI-75 by visit
 
• Percentage of participants with an IGA score of 0 or 1 and a reduction <math>\geq 2</math> points from baseline by visit
 
• Percentage change in EASI total by visit
 
• Change in EASI total by visit
 
• Percentage of participants achieving EASI-90 by visit
 

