#### Type of Participant and Disease Characteristics

2. Participants who are self-reported race other than White, including but not limited to persons who self-identify as Black or African American, American Indian or Alaska Native, Asian, Native Hawaiian, or Other Pacific Islander.
3. Participants who are Fitzpatrick phototype IV-VI (Section 8.1.15).
4. Have chronic AD (according to American Academy of Dermatology Consensus Criteria; Eichenfield et al. 2014; Appendix 7, Section 10.7) that has been present for  $\geq 1$  year before screening visit.
5. Have EASI  $\geq 16$  at the baseline visit.
6. Have Investigator's Global Assessment (IGA) score  $\geq 3$  (scale of 0 to 4) at the baseline visit.
7. Have  $\geq 10\%$  BSA of AD involvement at the baseline visit.
8. Have a history of inadequate response to treatment with topical medications; or determination that topical treatments are otherwise medically inadvisable.

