#### **8.1.13. Work Productivity and Activity Impairment Questionnaire-Atopic Dermatitis (WPAI-AD)**

The Work Productivity and Activity Impairment Questionnaire-Atopic Dermatitis (WPAI-AD) is a participant-reported, 6-item questionnaire that records impairment due to AD over the past 7 days in adolescents and adults. The WPAI-AD consists of 6 items grouped into 4 domains: absenteeism (work time missed), presenteeism (impairment at work/reduced on the job effectiveness), work productivity loss (overall work impairment/absenteeism plus presenteeism), and activity impairment. Absenteeism, presentism, and work productivity will only be reported by those who are currently employed (working for pay) at the time of the scale completion. The recall period for the scale is over the past 7 days. Scores are calculated as impairment percentages (Reilly et al. 1993), with higher scores indicating greater impairment and less productivity.

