Secondary Endpoints: 
 Percentage of participants achieving EASI-75 at Week 24 Percentage of participants with an IGA score of 0 or 1 and a reduction ≥ 2 points from baseline to Weeks 16 and 24 Percentage change in EASI total from baseline to Weeks 16 and 24 Change in EASI total from baseline to Weeks 16 and 24 Percentage of participants achieving EASI 90 at Weeks 16 and 24 Percentage of participants with a Pruritus NRS of ≥ 4 points at baseline who achieve a 4-point reduction at Weeks 16 and 24 Percentage of participants with a Pruritus NRS ≥ 3 points at baseline who achieve at least 3-point reduction at Weeks 16 and 24 Percentage change in Pruritus NRS score from baseline to Weeks 16 and 24 Percentage of participants with a Sleep-Loss Scale score of ≥ 2 points at baseline who achieve a 2-point reduction at Weeks 16 and 24 Percentage change in Sleep-Loss Scale score from baseline to Weeks 16 and 24 Percentage of participants with a Skin Pain NRS of ≥ 4 points at baseline who achieve a 4-point reduction from baseline to Weeks 16 and 24 Change in POEM from baseline to Weeks 16 and 24 Change in DLQI from baseline to Weeks 16 and 24 in participants ≥ 16 years of age at baseline Change in cDLQI from baseline to Weeks 16 and 24 in participants < 16 years of age at baseline Percentage of participants with a DLQI of ≥ 4 points at baseline who achieve a ≥ 4-point improvement in DLQI at Weeks 16 and 24 in participants ≥ 16 years at baseline
Exploratory Endpoints: 
 Change from baseline in body surface area (BSA) by visit Percentage change in PO-SCORAD from baseline by visit Change in Post-inflammatory Dyschromia Scale (PDS) from baseline by visit Percentage change in ADCT from baseline by visit Using WPAI-AD by visit, change in baseline in 
 o absenteeism in those who are currently employed (working for pay) o presenteeism in those who are currently employed (working for pay) o overall work impairment in those who are currently employed (working for pay), and o impairment in activities (all participants) Percentage of participants with an F-IGA score of 0 or 1 and a reduction ≥ 2 points from baseline by visit Lichenification change from baseline (calculated from EASI) Participant satisfaction change from baseline (1 question)

- Percentage of participants achieving EASI-75 by visit

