5.11 Efficacy Analyses

Table KGBP.5.4 includes the description and derivation of the efficacy measures and endpoints.

For categorical parameters, the number and percentage of patients in each category will be presented, as well as a 90% Wilson-Score confidence interval for the percentage. For continuous parameters, descriptive statistics will include n (number of patients), mean, standard deviation, Q1, median, Q3, minimum, and maximum. These summaries will be provided for the data as-observed and after implementation of LOCF and MCMC-MI imputation as described in Sections 5.4.2 and 5.4.3.

The IGA, F-IGA, EASI, BSA, Pruritus NRS, Skin Pain NRS, and Sleep-Loss Scale will be reported by clinic visit.

Table KGBP.5.4. Description and Derivation of Efficacy/Health Outcomes Measures and Endpoints

Measure	Description	Variable	Derivation/Comment	Imputation Approach if Missing Components
Investigator's Global Assessment (IGA)	The IGA is a static assessment and rates the severity of a patient's AD. The IGA is comprised of a 5-point scale ranging from 0 (clear) to 4 (severe), and a score is selected using descriptors that best describe the overall appearance of the lesions at a given time point.	IGA score	Single item. Range: 0-4 0 represents "clear" 4 represents "severe"	Single item, missing if missing
		• IGA (0,1) with ≥ 2 -point improvement ^a IGA (0)	• Observed score of 0 or 1 and change from baseline ≤ 2 Observed score of 0	Missing if baseline or observed value is missing Single item, missing if missing
Face-Investigator's Global Assessment (F-IGA)	The F-IGA is a static assessment and rates the severity of a patient's AD on the face. The F-IGA is comprised of a 5-point scale ranging from 0 (clear) to 4 (severe), and a score is selected using descriptors that best describe the overall appearance of the lesions at a given time point.	F-IGA Score	Single item. Range: 0-4, 0 represents "clear", 4 represents "severe"	Single item, missing if missing
		F-IGA (0,1)	Observed score of 0 or 1	Missing if baseline or observed value is missing
		F-IGA (0)	Observed score of 0	Single item, missing if missing

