WPAI-AD	The Work Productivity and Activity Impairment Questionnaire–Atopic Dermatitis is a participant-reported, 6-item questionnaire that records impairment due to AD over the past 7 days in adolescents and adults	Percent change from baseline in WPAI AD Absenteeism Score Percent change from baseline in WPAI AD Presenteeism Score Percent change from baseline in WPAI AD Work Productivity Loss Score Percent change from baseline in WPAI AD Activity Impairment Score	The Work Productivity and Activity Impairment Questionnaire– Atopic Dermatitis consists of 6 items grouped into 4 domains: absenteeism (work time missed), presenteeism (impairment at work or reduced on the job effectiveness), work productivity loss (overall work impairment or absenteeism plus presenteeism), and activity impairment. Absenteeism, presentism, and work productivity will only be reported by those who are currently employed (working for pay) at the time of the scale completion. The recall period for the scale is over the past 7 days. Scores are calculated as impairment percentages (Reilly et al. 1993), with higher scores indicating greater impairment and less productivity	If 1 question in a domain is missing, that domain is missing.

Abbreviations: AD = atopic dermatitis; HRQoL = health-related quality of life; NA = not applicable; QoL = quality of life.

a Secondary endpoints.

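### SAP Table KGBP.5.4 drops the 2-point reduction from the F-IGA response and turns WPAI-AD change into percent change, against the protocol and the SAP's own endpoint list

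*SAP*

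**What the plan says.** **F-IGA.** The exploratory endpoint in protocol Section 3 begins "Percentage of participants with an F-IGA score of 0 or 1 and a reduction" and goes on to require at least 2 points from baseline, by visit. SAP Table KGBP.3.1 repeats it. The derivation table, KGBP.5.4 in SAP Section 5.11, has three F-IGA variables: the score, F-IGA (0,1) and F-IGA (0). F-IGA (0,1) is derived as "Observed score of 0 or 1", with no change condition, yet its missing-data rule reads "Missing if baseline or observed value is missing". The overall IGA row directly above does carry a change-from-baseline condition.

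**WPAI-AD.** SAP Table KGBP.3.1 introduces the endpoint with "Using WPAI-AD by visit, change in baseline in" and then lists absenteeism, presenteeism, overall work impairment and activity impairment. Protocol Section 3 has the same list, with the last item given as "impairment in activities (all participants"). Table KGBP.5.4 offers only percent change for all four, for example "Percent change from baseline in WPAI AD Activity Impairment Score". Protocol Section 8.1.13 describes the scale: "Scores are calculated as impairment percentages".

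Neither document gives a reason for either difference.

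**The concern.** Programmers work from the derivation table. If they follow it, the reported F-IGA result will not be the protocol endpoint, because no variable in the table carries the reduction.

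The missing condition matters more for the face than for the whole body. Protocol Section 5.1 requires an overall IGA of at least 3 at baseline, so anyone who reaches IGA 0 or 1 has already dropped at least 2 points. There is no such threshold for F-IGA, so participants with a clear or almost clear face can enter and count as responders by staying that way. F-IGA is one of the novel endpoints that the protocol rationale puts forward for this population, so an inflated rate would be noticed and quoted.

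For WPAI-AD, percent change divides by a score that can be zero. The table has no rule for that case. The people affected can only stay at zero or get worse, so losing them is not neutral. Activity impairment is meant to cover every participant, so the loss is not confined to the employed.

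**Working it through.** **F-IGA: which score pairs count.** The scale runs from 0 to 4 (protocol Section 8.1.4). The pairs that end at 0 or 1 number 5 × 2 = 10. The protocol condition is visit − baseline ≤ −2.

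| Baseline | Visit 0 | Visit 1 |
|---|---|---|
| 0 | table only | table only |
| 1 | table only | table only |
| 2 | both | table only |
| 3 | both | both |
| 4 | both | both |

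The table's rule accepts 10 pairs and the protocol's accepts 5. The surplus pairs are 0→0, 0→1, 1→0, 1→1 and 2→1; one of them (0→1) is a worsening. For overall IGA, with baseline 3 or 4, all 4 pairs ending at 0 or 1 satisfy the condition. These counts show how the definitions differ; they are not shares of participants.

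**F-IGA: size of the excess.** Every protocol responder is also a responder under the table, and the denominator is the same. Hence

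excess = share starting and ending at 0/1 + share moving from 2 to 1.

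The documents give neither share. Assumed values:

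- 10% and 0%: 0.10 + 0 = 10 points
- 30% and 0%: 0.30 + 0 = 30 points
- 30% and 15%: 0.30 + 0.15 = 45 points

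If nobody falls in either group, the excess is zero.

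**Scale.** The SAP reports discrete efficacy endpoints with 90% Wilson intervals. At n = 80 and a 50% rate the interval is 40.96% to 59.04%, which reproduces SAP Table 4.2; the half-width is (59.04 − 40.96)/2 = 9.04 points. At n = 95, the protocol's current target, it is 41.68% to 58.32%, half-width 8.32. SAP Table 4.2 was built for EASI-75, so this shows only the precision of a 50% rate at these sample sizes.

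**WPAI-AD: the two measures can disagree in sign.** Hypothetical scores:

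| Baseline → visit | Change | Percent change |
|---|---|---|
| 10 → 20 | +10 | +100% |
| 60 → 30 | −30 | −50% |
| Mean of these two | −10 (better) | +25% (worse) |
| 0 → 20 | +20 | undefined |

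**WPAI-AD: effect of losing zero baselines.** Assume a share g has baseline 0 and stays at 0, while everyone else improves by 20 points. The mean change over all participants is (1 − g)(−20) + g·0:

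- g = 0.2: −16
- g = 0.4: −12
- g = 0.6: −8

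Dropping the zero-baseline group leaves −20 in every case. Both sides of this comparison use absolute change, so it isolates the selection effect and does not measure the whole effect of percent change. Both g and the 20 points are assumptions.

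**The case against.** The mismatches in wording are not in dispute. The case on the other side is that little follows from them.

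- *F-IGA (0,1) may be an extra variable.* Its label does not mention a 2-point improvement, and the table holds other variables outside the endpoint list, such as IGA (0) and DLQI (0,1). The endpoint itself is correctly stated in Table KGBP.3.1, so a programmer might still use that definition. This is possible, but the protocol endpoint then has no derivation row, and the row still needs repair. The missing-data rule, which calls on a baseline that the derivation never uses, suggests a dropped phrase.
- *Percent change may mean percentage points.* WPAI-AD scores are already percentages, and the row prints no formula. However, the same table defines percent change as a ratio to baseline for EASI and PO-SCORAD. Protocol Section 3 also separates percentage change (PO-SCORAD, ADCT) from change (WPAI-AD). If points were meant, nobody is lost and only the wording is wrong; the same edit settles it.
- *The sizes are assumed.* This stands. The documents contain no baseline F-IGA or WPAI-AD distribution, so the ranges are illustrations. The direction of the F-IGA error does not depend on them.
- *The endpoints are exploratory and nothing is tested.* This also stands, and it limits how serious the point is.

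**Conclusion.** The concern holds. As written, Table KGBP.5.4 contradicts both the protocol and the SAP's own endpoint list on both endpoints.

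For F-IGA, the rate under the table's rule can never be below the protocol rate, and it is above it whenever anyone starts and ends at 0/1 or moves from 2 to 1. The excess is 10 to 45 points under the assumed shares and cannot be fixed from the documents. For WPAI-AD, read as a ratio, participants unimpaired at baseline drop out of the summary, including any who worsen. The reported n would show that some are missing, but not that all of them are non-improvers.

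Both endpoints are exploratory and descriptive. EASI-75 is derived correctly in the same table, and the sample size is untouched. The table should be corrected, but the main result is not at risk.

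**What to change.** In Table KGBP.5.4:

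1. Define the F-IGA response as an observed score of 0 or 1 **and** a change from baseline of −2 or lower, with all participants in the denominator as in the protocol. The existing missing-data rule then fits.
2. Derive the four WPAI-AD domains as observed minus baseline, in percentage points. This needs no rule for a zero baseline.

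A useful but optional addition is an F-IGA summary among participants with baseline F-IGA of at least 2, because those who start at 0 or 1 cannot meet the protocol definition.

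The cost is two row edits before programming, plus one supplementary summary if it is wanted. The reported F-IGA rate may be lower than under the current rule. The SAP needs a revision in any case, since Sections 4.1 and 4.1.1 still give about 80 participants against the protocol's 95.

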5.1.2 General Considerations for Analyses

All analyses will be descriptive. Frequencies, percentages, and 90% Wilson-Score CIs for percentages will be reported for discrete efficacy endpoints. Mean, standard deviation, minimum, Q1, median, Q3, maximum, and the number of participants will be reported for continuous

efficacy endpoints. AEs, discontinuation, and other categorical safety data will be summarized using frequencies and percentages. Continuous vital signs, body weight, and other continuous safety variables including laboratory variables will be summarized descriptively as well.

Baseline

Baseline will be defined as the last available value before the first injection for efficacy and health outcome analyses. In most cases, this will be the measure recorded at the baseline visit (Day 1). If the patient does not take any injection, the last available value on or prior to treatment assignment date will be used. Change from baseline will be calculated as the visit value of interest minus the baseline value.

For Pruritus Numeric Rating Scale (NRS), Skin Pain NRS, and Sleep-Loss due to Pruritus collected via eDiary, the baseline period is the 7-day window prior to the first injection. A patient must have responses on at least 4 of 7 days to calculate a baseline weekly mean. If a patient has 3 or fewer responses, the baseline mean value will be considered missing.

For the safety analyses, the following baselines will be used. For safety analyses using a baseline period, the baseline period is defined as the time from the screening visit to the date/time of the first injection.

- TEAEs: baseline will be all results recorded during the baseline period.
- Treatment-emergent abnormal laboratory and vital signs results: baseline will be all results recorded during the baseline period.
- Change from baseline to last post-baseline observation or to each scheduled postbaseline visit for laboratory and vital signs results: baseline will be the last scheduled non-missing assessment recorded during the baseline period.

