Body Surface Area (BSA) Affected by AD	
The BSA assessment estimates the extent of disease or skin involvement with respect to AD and is expressed as a percentage of total body surface. BSA will be determined by the investigator or designee using the patient palm = 1% rule.
	BSA score	
BSA Total = BSA_{head and neck} + BSA_{trunk} + BSA_{upper limbs} + BSA_{lower limbs}
	NA: partial assessments cannot be saved.
		Change from baseline in BSA score ^a	
Change from baseline: observed BSA score - baseline BSA score
	Missing if baseline or observed value is missing.
Dermatology Life Quality Index (DLQI)	
The DLQI is a validated, dermatology-specific, patient-reported measure that evaluates a patient's HRQoL. This questionnaire has 10 items that are grouped in 6 domains, including symptoms and feelings, daily activities, leisure, work and school, personal relationships, and treatment. The recall period of this scale is over the "last week".
 
Response categories and corresponding scores are:
	DLQI total score	
A DLQI total score is calculated by summing all 10 question responses and has a range of 0-30 (less to more impairment) (Finlay and Khan 1994; Basra et al. 2008).
	
Score of 1 unanswered question = 0; If 2 or more questions are missing, the total score is missing. Note: #7B could be a valid missing while #7A is not "No." That is, #7 should be considered as 1 question.

		DLQI (0,1)	
A DLQI (0,1) response is defined as a postbaseline DLQI total score of 0 or 1. A DLQI total score of 0-1 is considered as having no effect on a patient's HRQoL (Khilji et al. 2002; Hongbo et
	Missing if DLQI total score is missing

Very much = 3 A lot = 2 A little = 1 Not at all = 0 Not relevant = 0
 
Scores range from 0-30, with higher scores indicating greater impairment of QoL. A DLQI total score of 0-1 is considered as having no effect on a patient's HRQoL (Hongbo et al. 2005), and a 4-point change from baseline is considered as the minimal clinically important difference threshold (Khilji et al. 2002; Basra et al. 2015).
	
al. 2005).
 
4-point improvement^a
	
Change from baseline \leq4
	
Missing if baseline is missing or observed value is missing.

	
DLQI total score and domain scores change from baseline^a
	
Calculated as: observed DLQI (total score or domain scores) - baseline DLQI (total score or domain scores)
	
Missing if baseline or observed value is missing

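### SAP Table KGBP.5.4 prints the DLQI 4-point response, a secondary endpoint, as change from baseline ≤ 4, although change is visit minus baseline and the rule needs ≤ −4

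*SAP*

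**What the plan says.** SAP 5.1.2 gives one rule for all change scores: "Change from baseline will be calculated as the visit value of interest minus the baseline value". The DLQI row of Table KGBP.5.4 repeats it: "Calculated as: observed DLQI (total score or domain scores) - baseline DLQI (total score or domain scores". The row also fixes the direction of the scale, "with higher scores indicating greater impairment of QoL", and says that "a 4-point change from baseline is considered as the minimal clinically important difference threshold".

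The variable in that row is labelled as a 4-point improvement and footnoted as a secondary endpoint. Its derivation reads "Change from baseline" ≤ 4, with no minus sign. SAP Table KGBP.3.1 and Protocol Section 3 define the endpoint as a 4-point or larger "improvement in DLQI at Weeks 16 and 24 in participants" aged 16 or over, among those with a baseline DLQI of at least 4.

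Four further cut-offs in the same table lack the sign: POEM 4-point improvement (≤ 4), PO-SCORAD75 (≤ 75), PO-SCORAD90 (≤ 90) and the IGA response, "Observed score of 0 or 1 and change from baseline" ≤ 2. Three cut-offs carry it: EASI-75 (≤ −75), EASI-90 (≤ −90) and CDLQI 4-point improvement (≤ −4).

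**The concern.** On every one of these scales a fall is good, and change is visit minus baseline, so improvement is a negative number. A positive cut-off with a less-than-or-equal sign admits small improvements, no change and some worsening. For DLQI only a rise of 5 points or more would fail.

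This matters most for DLQI, because response at Weeks 16 and 24 is a protocol secondary endpoint. SAP 5.11 names Table KGBP.5.4 as the place where measures and endpoints are derived. The main analysis of the secondary endpoints is as observed (SAP 5.2.3, 5.2.4 and 5.4.1), and for that analysis the table holds the explicit numerical rule. The correct wording in SAP 5.4.3 sits in the multiple-imputation section. If each place were programmed as written, the as-observed and imputed results for one endpoint would follow different rules.

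**Working it through.** The plan states no figure that depends on these cut-offs, so there is none to reproduce. The check compares each printed rule with the sign-corrected one.

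**Inputs.** Change = visit − baseline (SAP 5.1.2). DLQI runs 0–30, with baseline at least 4 for the endpoint (SAP Tables KGBP.5.4 and KGBP.3.1). POEM runs 0–28 (Table KGBP.5.4). Entry IGA is at least 3, "scale of 0 to 4) at the baseline visit" (Protocol 5.1).

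| Variable | As printed | With sign | Status |
|---|---|---|---|
| DLQI 4-point | ≤ 4 | ≤ −4 | secondary endpoint |
| POEM 4-point | ≤ 4 | ≤ −4 | not a protocol endpoint |
| PO-SCORAD75 / 90 | ≤ 75 / ≤ 90 | ≤ −75 / ≤ −90 | not protocol endpoints |
| IGA (0,1) with 2-point improvement | ≤ 2 | ≤ −2 | secondary endpoint |

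**DLQI, single values.** Changes of −3, 0, +3 and +4 all satisfy ≤ 4, and none satisfies ≤ −4. A change of +5 fails both.

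**DLQI, all integer score pairs.** There are 27 baselines (4 to 30) × 31 visit scores = 837 pairs. The corrected rule accepts 378 and the printed rule 584. The difference, 584 − 378 = 206, consists of 98 worsening pairs (of 351), 27 unchanged pairs, and 81 pairs (27 × 3) improving by 1 to 3 points: 98 + 27 + 81 = 206. These count possible scores and are not expected response rates.

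**POEM, all integer pairs.** 29 × 29 = 841 pairs. The corrected rule accepts 325 and the printed rule 541, including 106 of 406 worsening pairs.

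**PO-SCORAD.** A change of 0% or +75% meets the printed PO-SCORAD75 rule, and +90% meets the printed PO-SCORAD90 rule. Every printed PO-SCORAD75 responder is then also a PO-SCORAD90 responder, which reverses the proper nesting.

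**IGA.** With baseline 3 or 4 and a visit score of 0 or 1, the largest possible change is 1 − 3 = −2. Both rules therefore classify every eligible participant alike.

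**Imputed values.** SAP 5.4.3 sets participants who stop for lack of efficacy to their baseline value, so their change is 0. Since 0 ≤ 4, the printed DLQI rule would turn these intended failures into responders if it were applied to the imputed data. The same holds under LOCF for a participant with no postbaseline score, because SAP 5.4.2 then carries the baseline value.

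**Illustrative response rates.** Assume DLQI change is normal with mean μ and SD σ (neither is in the documents), with a continuity correction:

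- printed rate = Φ((4.5 − μ)/σ)
- corrected rate = Φ((−3.5 − μ)/σ)

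| μ, σ | Printed | Corrected |
|---|---|---|
| −8, 7 | Φ(1.786) = 96% | Φ(0.643) = 74% |
| −4, 7 | Φ(1.214) = 89% | Φ(0.071) = 53% |
| 0, 6 | Φ(0.750) = 77% | Φ(−0.583) = 28% |

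Over means of −4 to −10 and SDs of 5 to 9, the printed rule gives 83% to more than 99%, and the corrected rule 52% to 90%.

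**The case against.** **The signs may have been lost in reading the PDF.** The SAP's reference list drops hyphens that the protocol's list keeps (one cited review has page range 2031 in the SAP and 20-31 in the protocol), and SAP 5.13.2 has displaced hyphens. The less-than-or-equal direction also makes sense only with a negative cut-off. Against this, the reference examples are unrelated strings. In Table KGBP.5.4 itself the subtraction signs in the DLQI, POEM and PO-SCORAD rows survive, as do the negative PDS grades and the EASI and CDLQI cut-offs. Loss in single cells still cannot be excluded, so the source PDF must be checked.

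**The intent is clear elsewhere.** The cell labels say improvement, and the PO-SCORAD cells state the right percentage improvement beside the wrong inequality. SAP 5.4.3 and its seed table require a DLQI reduction of at least 4 points, and SAP 5.4.3 works an IGA example in the right direction. This stands. A reader might infer that unchanged or worse participants will be counted as responders. The documents do not support that, because it happens only if the inequality is coded against its own label.

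**The scope is narrow.** A reader might also infer that four measures, or efficacy results generally, are compromised. They are not. IGA is unaffected in practice, and POEM 4-point and PO-SCORAD75/90 responses appear neither among the protocol's endpoints nor in SAP Table KGBP.3.1. The study is descriptive and tests no hypothesis.

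**Conclusion.** The point holds for one endpoint. As the text stands, the derivation of the secondary DLQI response contradicts the SAP's definition of change, the cell's own label, the matching CDLQI row, SAP 5.4.3 and the protocol. Coded literally, it would credit no change and worsening of up to 4 points as response. The POEM and PO-SCORAD cut-offs have the same fault with less consequence, and the IGA cut-off has it with none.

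The size is conditional on literal coding and on an assumed DLQI distribution. The normal model also ignores the 0–30 bounds and the baseline restriction, so 96% against 74% is an illustration and not a forecast. Confidence is moderate, because the source PDF could show that some or all of the signs are present. The error is worth correcting because it sits in the derivation table for a secondary endpoint, but it does not touch the primary result.

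**What to change.** 1. Check Table KGBP.5.4 in the source PDF for the minus signs.
2. Where they are absent, set the cut-offs to DLQI change ≤ −4, POEM change ≤ −4, PO-SCORAD75 percent change ≤ −75, PO-SCORAD90 percent change ≤ −90 and IGA change ≤ −2, in line with the EASI and CDLQI rows.
3. Confirm that the as-observed, LOCF and MCMC-MI programs all use these cut-offs, with DLQI first.

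The cost is at most five cell corrections and a short code check. Data collection, sample size and estimands do not change. If the programs already use the negative cut-offs, no result changes either.
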